All subjects will be followed annually through 36 months post procedure (Table 1), except Crossover subjects. Subjects and blinded study personnel will be unblinded to the randomization assignment at 6 months. Control (sham) subjects may be offered renal denervation therapy (crossover) after their 6-month follow-up visit, according to Section F.10. Crossover subjects will return for office visits at 1, 3, 6, 12 and 24 months post-renal denervation procedure (Table 2).

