- d. **Office Blood Pressure** measurements will be obtained in accordance with Appendix L.7. The average office blood pressure value will be used as the baseline value for comparison with follow-up visit office blood pressure values. Subjects with an office systolic blood pressure  $\geq 150$  and  $< 180$  mmHg and an office DBP  $\geq 90$  mmHg are eligible to continue the screening process.
- e. **Laboratory Tests:**
  - **Basic metabolic panel Chem-7 (blood):** serum-creatinine, sodium, potassium, blood urea nitrogen (BUN), bicarbonate, chloride and glucose. Bicarbonate will not be measured for subjects enrolled in Japan and Europe.

- **Lipid Panel and hs-CRP (blood):** total cholesterol, HDL, LDL, and triglycerides, as well as high sensitive-C reactive protein test are intended to evaluate a subject's cardiovascular risk profile. High-sensitivity CRP is not required to be measured for subjects enrolled at sites where high-sensitivity CRP test cannot be locally performed.
- **Uric Acid (blood):** This test is intended to potentially identify a marker for the renal denervation therapy responders.
- **eGFR** will be calculated from the serum-creatinine in the Chem-7 panel for eligibility criteria by using the 4 variable Modification of Diet in Renal Disease (MDRD) Formula or the local Japanese criteria for subjects enrolled in Japan. The equation for estimated Glomerular Filtration Rate (eGFR) calculation method for Japanese is as follows:

$$\text{eGFR (mL/min/1.73 m}^2\text{)} = 194 \times (\text{sCr})^{-1.094} \times (\text{Age})^{-0.287} \times (0.739 \text{ if female})$$

Japanese Society of Hypertension Guidelines (JSH 2014), Hypertension Research (2014) 37, 266–278.

**Note:** If eGFR  $\geq 42$  and  $< 45$  mL/min/1.73m^2 then patient can be retested after hydration with a single, repeat test within two weeks.

- **hCG** pregnancy test in blood/urine for female subjects who are not post-menopausal

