  - **Renin and Aldosterone (blood):** Samples should be collected in the morning after the patient has been out of bed for  $\geq 2$  hours and after resting quietly sitting for a minimum of 5 minutes but preferably 30 minutes. The time of day and subject's position (standing, sitting, or lying down) when the blood sample is collected should be documented and the same time of day ( $\pm 2$  hours) and subject position should be used for collection of blood samples for determination of renin and aldosterone at later time points in the study.
  - **Drug testing (urine/blood)** to ensure medications are no longer present in the subject's system. A urine sample will be collected, preferably using the subject's first morning urine. A blood sample will be collected at the time of the visit.
- f. **24-hour Ambulatory Blood Pressure Monitoring** will be applied at the conclusion of Screening Visit 2 to confirm subject's baseline blood pressure. This value will be utilized as the baseline value for calculating change in 24-hour ABPM at various time points post-procedure. Subjects with a 24-hour systolic ABPM of  $< 140$  or  $\geq 170$  mmHg after completion of the screening visit will be exited from the study. Subjects with a 24-hr systolic ABPM of  $\geq 140$  and  $< 170$  mmHg are eligible to continue to the randomization (procedure or control) visit. A single repeat measurement is allowed in case of the following: 1.) a technical issue with the blood pressure monitor or failure to follow ABPM instructions, or 2.) if a valid number of readings is not obtained, or 3.) if the 24-hr systolic ABPM measured

135 - <140 mmHg or 170-175 mmHg. ABPM must be conducted according to the guidelines in Appendix L.7. If ABPM is repeated office blood pressure and drug testing must be repeated on day the ABPM is applied.

- g. **Adverse Event Reviews** will be completed to document adverse events that occur after enrollment.
- h. **Baseline Renal Imaging** Submit a baseline Duplex Ultrasound, CT, or MRA if obtained per standard of care prior to procedure within one year from the date of the screening visit 1 and upload via Intelemage or send via courier.

Subjects determined to not be eligible for randomization will be exited from the study, as described in the Subject Exit from Study section of this Clinical Investigation Plan.

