### F.9 Medication Re-Introduction for Subjects with 3M Systolic OBP $\geq 140$ mmHg

Upon completion of a valid ABPM at the 3 month follow-up visit, subjects with an office SBP  $< 140$  mmHg do not need to be followed up for study purposes until the 6 month follow-up visit. Subjects with an office SBP  $\geq 140$  mmHg will begin an antihypertensive medication regimen of one or more of the following classes individually or in a combination pill with dosing at the discretion of the study investigator:

- ACE/ARB
- Calcium Channel Blocker
- Thiazide-Type Diuretic

Subjects will return at 4 months ( $\pm$  7 days) to perform a clinical assessment and obtain an Office Blood Pressure according to the guidelines in Appendix L.7.

- The investigator may utilize his or her discretion in modifying the antihypertensive regimen.
- Any modification to the antihypertensive medication regimen must be documented on the eCRFs.

To provide the appropriate oversight for study subjects, the visit schedule between the required 4-month and 6-month visits may need to be adapted to account for a subject's clinical status, complexity of the medication regimen, and/or the subject's blood pressure. If additional changes to the antihypertensive medication regimen are made between 3 and up to 6 months post-procedure, complete an unscheduled follow-up visit, and obtain an Office Blood Pressure according to the guidelines in Appendix L.7. In addition, all medication changes are to be documented on the eCRF. All medication used should be commercially available in the respective geographies and compliant with local labeling.

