### **Baseline Crossover Data:**

Control subjects who are coming in for their scheduled 6, 12, 24, 36-month or Unscheduled follow-up visits do not need to come in for a crossover baseline visit if all required crossover baseline procedures occurred during the respective follow-up visit, as listed below. An in-office visit is required for the baseline crossover visit assessments. Note, if the lipid panel, hs-CRP and uric acid were collected at SV2, these tests will not be required to be repeated. If the lipid panel, hs-CRP and uric acid was not collected at SV2, they will need to be collected within 30 days prior to the crossover procedure. For subjects accepting crossover at their 6-month visit, the 6-month DUS is not needed, if the subject has the crossover procedure within 30 days of the visit.

- a) **Clinical Assessment** will be conducted.
- b) **Office Blood Pressure** measurements will be obtained in accordance with Appendix L.7.
- c) **Laboratory Tests:**
  - **Basic metabolic panel Chem-7 (blood):** serum-creatinine, sodium, potassium, blood urea nitrogen (BUN), bicarbonate, chloride and glucose. Bicarbonate will not be measured for subjects enrolled in Japan and Europe.
  - **Lipid Panel and hs-CRP (blood) (prior to procedure, If not already collected at SV2):** total cholesterol, HDL, LDL, and triglycerides, as well as high sensitive-C reactive protein test are intended to evaluate a subject's cardiovascular risk profile. High-sensitivity CRP is not required to be measured for subjects enrolled at sites where high-sensitivity CRP test cannot be locally performed.
  - **Uric Acid (blood) (prior to procedure, If not already collected at SV2):** This test is intended to potentially identify a marker for the renal denervation therapy responders.
  - **eGFR** will be calculated from the serum-creatinine in the Chem-7 panel for eligibility criteria by using the 4 variable Modification of Diet in Renal Disease (MDRD) Formula or the local Japanese criteria for subjects enrolled in Japan.
  - **hCG (prior to procedure)** pregnancy test in blood/urine for female subjects who are not post-menopausal.
  - **Drug testing (urine/blood)** to ensure prescribed medications are present in the subject's system. A urine sample will be collected, preferably using the subject's first morning urine. A blood sample will be collected at the time of the visit.

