#### 9.9.8. Other Secondary Efficacy Endpoints

The following additional secondary efficacy endpoints will be assessed:

- Change in systolic blood pressure (SBP) from baseline (Screening Visit 2) as measured by 24-hour Ambulatory Blood Pressure Monitoring (ABPM) at 3, 6, 12, 24 and 36 months post-procedure.
- Change in office systolic blood pressure from baseline (Screening Visit 2) at 1, 3, 6, 12, 24 and 36 months post-procedure.
- Incidence of achieving target office systolic blood pressure (SBP <140 mmHg) at 1, 3, 6, 12, 24 and 36 months post-procedure.
- Change in office diastolic blood pressure from baseline (Screening Visit 2) at 1, 3, 6, 12, 24 and 36 months post-procedure.
- Change in diastolic blood pressure from baseline (Screening Visit 2) as measured by 24-hour Ambulatory Blood Pressure Monitoring (ABPM) at 3, 6, 12, 24 and 36 months post-procedure.

RDN vs. control groups will be compared out to 6-months post randomization, prior to the crossover procedure. Statistical comparisons will be performed using the independent samples t-test for continuous endpoints and Fisher's exact test for categorical endpoints. In addition, two-sided 95% confidence intervals of the difference between RDN and control groups will be presented. Changes in blood pressure measurements from baseline to follow-up within each treatment group will be assessed using paired t-tests. Two-sided 95% confidence intervals of the mean change from baseline will be presented for each treatment group. Analysis of Covariance (ANCOVA) models, adjusting the treatment effect for the baseline BP measurements will also be applied to all continuous secondary endpoints.

RDN vs. Crossover vs. Non-Crossover groups will be compared out to 36 months post-procedure for the RDN and Non-Crossover groups and out to 24 months for the Crossover group using chi-square tests for categorical data and ANOVA for continuous data.

Changes in blood pressure measurements from baseline to follow-up within each group will be assessed using paired *t*-tests. Two-sided 95% confidence intervals of the mean change from baseline will also be presented for each group.

The secondary efficacy analyses will be presented for all the study populations defined in section 9.1.3.

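### SAP 9.9.8 gives the Crossover group no blood pressure baseline other than the off-drug Screening Visit 2, so by default its within-group change mixes re-introduced drugs, elapsed time and denervation.

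*SAP*

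**What the plan says.** **Endpoint definition.** SAP 9.9.8 lists changes in office and 24-hour systolic and diastolic pressure, each anchored to SV2. The office systolic item reads "Change in office systolic blood pressure from baseline (Screening Visit 2) at 1, 3, 6, 12, 24 and 36 months post-procedure".

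**Analyses under that definition.** RDN is compared with control to 6 months. After that, RDN, Crossover and Non-Crossover are compared, with Crossover followed "out to 24 months for the Crossover group using chi-square tests for categorical data and ANOVA for continuous data". The section then adds "Changes in blood pressure measurements from baseline to follow-up within each group will be assessed using paired" t-tests, with a 95% confidence interval for the mean change in each group. SAP 9.9.9 repeats the paired tests and intervals.

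**Protocol baseline.** Section F.5 (Screening Visit 2) says of office pressure: "The average office blood pressure value will be used as the baseline value for comparison with follow-up visit office blood pressure values". Of the ambulatory reading it says: "This value will be utilized as the baseline value for calculating change in 24-hour ABPM at various time points post-procedure". Drug testing at SV2 is there to confirm that antihypertensive drugs are absent.

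**Between SV2 and crossover.** Under Protocol F.9, subjects with office SBP of 140 mmHg or more at 3 months "will begin an antihypertensive medication regimen of one or more of the following classes individually or in a combination pill". Under F.10, controls may cross over at or after the 6-month visit, including from the 12-, 24- or 36-month visit or an unscheduled visit. Their clock then restarts: "Crossover subjects will return for office visits at 1, 3, 6, 12 and 24 months post-renal denervation procedure" (Protocol synopsis, Treatment).

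**The crossover Baseline.** Protocol F.10 says "An in-office visit is required for the baseline crossover visit assessments". The visit covers office pressure, drug testing to confirm that prescribed drugs are present, and witnessed pill intake before ABPM. Protocol Tables 2 and 5 mark office pressure, 24-hour ABPM, Chem-7 and drug testing at Baseline. SAP 9.1.4 describes when the visit is needed and when a scheduled visit can replace it. No SAP analysis refers to the pressures measured there.

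**The concern.** A paired test on the Crossover group is naturally read as what happened after the crossover denervation. That reading needs a reference value taken shortly before the procedure and on the same drug background. SV2 is neither. It precedes crossover by about six months at least and by about three years at most, and it was taken with drugs withdrawn. Many controls will have restarted drugs in between.

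If SV2 is used, the Crossover change has three parts: the effect of re-introduced drugs, drift and regression to the mean since SV2, and whatever denervation adds. The paired p-value and confidence interval cannot separate them. They could show a clear fall even if denervation did nothing. What is at stake is how the long-term crossover results are interpreted. The trial's success criteria are not at stake.

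**Working it through.** The documents give no sample size, power or expected change for the Crossover analysis, so there is no plan figure to reproduce. What follows is an illustration.

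**Step 1: which baseline applies.** SAP 9.9.8 ties change to SV2 in the endpoint list. Its within-group sentence says only baseline, and no other value is assigned to that word for the Crossover group. Someone programming from the text would use SV2.

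**Step 2: how many controls would restart drugs.** From SAP Table 4, control change in office SBP is -2.54 mmHg, SD 16. The SV2 mean *m* is an assumption. With 3-month SBP ~ N(*m* - 2.54, 16²), the share at or above 140 is 1 - Φ((140 - (*m* - 2.54))/16).

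| Assumed *m* (mmHg) | z | Share ≥140 |
|---|---|---|
| 155 | -0.779 | 0.78 |
| 160 | -1.091 | 0.86 |
| 165 | -1.404 | 0.92 |
| 170 | -1.716 | 0.96 |

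Drawing SV2 instead from a normal (162, SD 8) cut to the eligible range of 150 to 180, and adding the same change distribution, gives 0.88.

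**Step 3: paired test from SV2 with zero denervation effect.** Let Δ be the mean fall on drugs across the group before crossover (assumed 5, 10 or 15 mmHg). SD 16 is borrowed from Table 4, *n* is assumed, and the test is two-sided at 0.05 (SAP 9.2). The noncentrality is δ = Δ/(16/√n) on n - 1 degrees of freedom, and the rejection probability is P(|T'| > t₀.₉₇₅), where T' is noncentral t. The standard errors are 16/√30 = 2.92 and 16/√60 = 2.07.

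| Δ (mmHg) | n = 30: δ, P(reject) | n = 60: δ, P(reject) |
|---|---|---|
| 5 | 1.71, 0.38 | 2.42, 0.66 |
| 10 | 3.42, 0.91 | 4.84, 0.997 |
| 15 | 5.13, >0.99 | 7.26, >0.99 |

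**Step 4: adding the planned sham drift.** With apparent change = -2.54 - (share on drugs × drug effect), a share of 0.75 and 5 mmHg give -2.54 - 3.75 = -6.29. A share of 1.0 and 15 mmHg give -2.54 - 15 = -17.54. The rejection probability then runs from 0.47 to above 0.99 at n = 25, and from 0.78 to above 0.99 at n = 50. Step 3 leaves this drift out and is the milder case.

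**Step 5: paired test from the crossover Baseline.** With zero denervation effect, an unchanged regimen, no time trend and no regression to the mean, the expected change is 0 and the test rejects about 5% of the time.

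**Step 6: the three-group ANOVA.** RDN and Non-Crossover subjects also restart drugs under F.9 and are also measured from SV2. If drug use is equal, the drug effect appears in all three groups and cancels in the contrasts. Moving only the Crossover group to an on-drug baseline would undo that. With a 10 mmHg drug effect in everyone, it would create a spurious difference of about 10 mmHg between Crossover and the other two groups.

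**The case against.** The strongest reply is that the plan never says in terms that Crossover change is taken from SV2. The within-group sentence leaves the word baseline open. The SV2 bullets run to 36 months, whereas crossovers are followed for 24. SAP 9.1.4 and Protocol Tables 2 and 5 use Baseline for the crossover visit. Protocol F.1 introduces the procedures that include F.5 as excluding crossovers. The SAP version history also records that the algorithms for selecting pressure and laboratory values were moved to the table specifications, which are not among these documents. All of this stands. It makes the finding one of a missing specification with a poor default, and it does not show that SV2 will in fact be used.

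Two stronger readings do not hold.

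- A reader might infer that every comparison involving crossovers credits drug effect to denervation. For the ANOVA, Step 6 shows otherwise: a common SV2 baseline is the safer choice there, and the remaining problems are unequal drug use and self-selection into crossover. Nor does the SAP attribute the Crossover change to denervation.
- A reader might extend the point to the creatinine endpoint, which is also anchored to SV2. That extension is weak. The event is adjudicated by the CEC, Protocol F.11 treats an already identified sustained rise separately, and an older rise counted after crossover would weigh against the device.

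SAP 9.9.10 does compare medication index scores between the groups, and 9.9.9 looks at adherence and pressure change. Neither adjusts the Crossover change for drugs or names a crossover Baseline score. For subjects who cross over from the 6-month visit, the 6-month score could serve.

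**Conclusion.** The point holds for the Crossover within-group changes, paired tests and confidence intervals in SAP 9.9.8 and 9.9.9. As the text stands they default to an off-drug reference taken long before denervation, while a suitable on-drug reference is collected and given no analysis role.

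The size is illustrative. With a mean drug-related fall of 5 to 15 mmHg, SD 16, 30 to 60 crossovers and no denervation effect, a significant fall from SV2 has probability about 0.38 to above 0.99, against about 0.05 from the crossover Baseline. The SV2 distribution, drug effect and number of crossovers are assumptions, and the SD is a 3-month planning value applied to a longer interval. Controls below 140 mmHg at 3 months need not be on drugs. The 0.05 figure also needs an unchanged regimen, no time trend, and no regression to the mean among those who choose crossover.

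The primary endpoints, the powered secondary endpoint and the RDN-versus-control comparisons to 6 months are unaffected.

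**What to change.** In SAP 9.9.8 and 9.9.9:

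1. State that the Crossover group's within-group change, paired test and confidence interval are calculated from the crossover Baseline, or from the scheduled or unscheduled visit that served as it under Protocol F.10.
2. Report the medication index at that visit and at each later visit beside the change.
3. Label any Crossover within-group change from SV2 as descriptive.
4. For the RDN, Crossover and Non-Crossover ANOVA, state SV2 as the common baseline and describe the comparison as non-randomised. Do not mix on-drug and off-drug baselines.
5. Leave the creatinine and eGFR event definitions as they are. At most, add a descriptive change from the crossover Baseline.

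If the table specifications already define a Crossover baseline, bring that definition into the SAP.

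The cost is a few sentences and one extra derivation, plus a medication index score at the crossover Baseline. The pressures are already collected. The reported Crossover fall will probably be smaller.

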#### *G.3.4 Criteria for unblinding*

Reasons for unblinding are:

- All randomized patients will be unblinded during the 6 month follow-up visit. The procedure will be offered to the randomized Control patients that continue to meet eligibility criteria after this visit.
- All randomized patients will immediately be unblinded in case of study termination.
- When a site is terminated, all randomized patients of this site will immediately be unblinded.

Unblinding must be documented including the signature of site study personnel, date and reason for unblinding and must be reported to the Clinical Study Manager. The unblinding will be documented on a separate file that can be found in the ISF.

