## H.6 Other Secondary Efficacy Endpoints

The following additional secondary efficacy endpoints will be assessed:

- Change in systolic blood pressure (SBP) from baseline (Screening Visit 2) as measured by 24-hour Ambulatory Blood Pressure Monitoring (ABPM) at 3, 6, 12, 24 and 36 months post-procedure.
- Change in office systolic blood pressure from baseline (Screening Visit 2) at 1, 3, 6, 12, 24 and 36 months post-procedure.
- Incidence of achieving target office systolic blood pressure (SBP <140 mmHg) at 1, 3, 6, 12, 24 and 36 months post-procedure.
- Change in office diastolic blood pressure from baseline (Screening Visit 2) at 1, 3, 6, 12, 24 and 36 months post-procedure.

- Change in diastolic blood pressure from baseline (Screening Visit 2) as measured by 24-hour Ambulatory Blood Pressure Monitoring (ABPM) at 3, 6, 12, 24 and 36 months post-procedure.

The efficacy endpoints will be compared between treatment groups using t-tests for continuous endpoints and Fisher's exact test for categorical endpoints. In addition, two-sided 95% confidence intervals of the difference between treatment groups will be presented. Changes in blood pressure measurements from baseline to follow-up within each treatment group will be assessed using paired t-tests. Two-sided 95% confidence intervals of the mean change from baseline will be presented for each treatment group.

Analysis of Covariance (ANCOVA) models, adjusting the treatment effect for the baseline BP measurements will also be presented.

These additional efficacy analyses will be presented for all the study populations defined in section H1.

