All the safety endpoints will be adjudicated by the Clinical Events Committee (CEC). The following algorithm will be used to evaluate the safety event rates: The denominator will include all subjects who either had a CEC adjudicated event prior to the time of interest (180 days for 6 months events, for example), or had last contact date that is beyond the lower window of the follow up (166 days for 6 month events, for example). The numerator will include all subjects who had CEC adjudicated events up to the time of interest (180 days for 6 months events, for example).

The secondary safety endpoints, out to 6-months follow-up, will be compared between treatment groups using Fisher's exact test. Two-sided 95% confidence intervals of the difference between treatment groups will also be presented.

After 6-months follow-up, control subjects may crossover (undergo renal denervation), and secondary safety endpoints will be summarized by group (RDN, Crossovers, Non-Crossovers). RDN vs. Crossover vs. Non-Crossover groups will be compared out to 36 months post-procedure for the RDN and Non-Crossover groups and out to 24 months for the Crossover group using chi-square tests for categorical data and ANOVA for continuous data.

The secondary safety analyses will be performed using the ITT population defined in section 9.1.3.1.

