#### 9.9.10. Medication Burden Analyses

Upon completion of a valid ABPM at the 3 month follow-up visit, subjects with an office SBP  $\geq$  140 mmHg will begin an antihypertensive medication regimen following protocol guidelines at the discretion of the study investigator. We will calculate the medication burden for each subject at 6, 12, 24 and 36-months using medication index scores that take into account the class, dose and frequency of each antihypertensive medication being taken.

- These scores will be compared between RDN and Control arms at the 6-month follow-up visit.
- At 12, 24 and 36 month follow-up visits, the scores will be compared between RDN, crossover and non-crossover arms.
- Multivariable predictors of medication index scores adjusting for treatment arm and BP measures will be performed.

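### After 6 months the SAP formally tests RDN against Crossover and Non-Crossover, two parts of one randomized arm divided after unblinding, so those p-values have no randomized interpretation

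*SAP*

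**What the plan says.** SAP 9.9.8 keeps the randomized comparison for the first half-year: "RDN vs. control groups will be compared out to 6-months post randomization, prior to the crossover procedure". It then changes the groups: "RDN vs. Crossover vs. Non-Crossover groups will be compared out to 36 months post-procedure for the RDN and Non-Crossover groups", with 24 months for Crossover and with chi-square and ANOVA as the tests.

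Three other SAP sections make the same switch:

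- **9.9.2, secondary safety:** "After 6-months follow-up, control subjects may crossover (undergo renal denervation), and secondary safety endpoints will be summarized by group (RDN, Crossovers, Non-Crossovers"), then compared "using chi-square tests for categorical data and ANOVA for continuous data". The section ends: "The secondary safety analyses will be performed using the ITT population defined in section 9.1.3.1".
- **9.9.9, additional objectives:** the same groups and tests, presented for the ITT set.
- **9.9.10, medication burden:** "At 12, 24 and 36 month follow-up visits, the scores will be compared between RDN, crossover and non-crossover arms". No test is named.

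SAP 9.2 makes two-sided 0.05 the default for declaring groups different. Nothing marks the three-group tests as descriptive.

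The protocol plans something else. H.6 says "The efficacy endpoints will be compared between treatment groups using t-tests for continuous endpoints" and Fisher's exact test for categorical ones. Its endpoints run to 36 months and it has no crossover split. H.3 does the same for secondary safety, with Fisher's exact test.

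On timing, protocol G.3.4 says "All randomized patients will be unblinded during the 6 month follow-up visit". Crossover is offered to control subjects after that.

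**The concern.** Randomization protects a comparison of RDN with the whole control arm. It does not protect a comparison of RDN with a part of that arm selected later. Crossover and Non-Crossover may differ in blood pressure, medication and health for reasons unrelated to denervation. An ANOVA or chi-square test across the three groups can then reject when the treatment does nothing.

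At stake are the statements on long-term efficacy, safety and medication burden at 12, 24 and 36 months. The SAP heads the chronic safety endpoints as compared between groups through 36 months. A reader of the report would take a significant three-group result as evidence about the device.

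**Working it through.** The documents give no sample size, power or error rate for the three-group comparison, so there is no plan figure to reproduce. The check is mainly a reading of the sections, followed by an illustration of size.

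**1. How the groups form.** Subjects are unblinded at 6 months (protocol C.5, G.3.4). Crossover then needs the agreement of subject and study doctor (protocol C.7) and passing anatomical, eGFR and pregnancy criteria (protocol F.10, SAP 9.1.4). All of this happens after randomization and open-label. The SAP plans no adjustment for it and no as-randomized comparison after 6 months.

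**2. Time origin and baseline.** The crossover procedure may follow the 6, 12, 24 or 36 month visit or an unscheduled one (SAP 9.1.4), and Crossover time runs from that procedure. A subject who crosses over at month 6 reaches the 24-month crossover visit at 6 + 24 = 30 months from the original procedure. From month 12 it is 12 + 24 = 36. The SAP does not say how a late crossover is classified before the switch. The listed endpoints use change from Screening Visit 2, which was off medication. Crossover subjects also have a baseline visit, possibly on medication (protocol F.10). The SAP does not say which baseline applies to them.

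**3. ITT label.** SAP 9.1.3.1 defines ITT as analysis by randomized treatment. Dividing the control arm by treatment later received does not follow that definition, yet 9.9.2 and 9.9.9 invoke it. Section 9.9.8 instead refers to all populations of 9.1.3.

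**4. SAP against protocol.** H.3 and H.6 compare two treatment groups; the SAP compares three after month 6. SAP 9.13 records no change to the planned analysis.

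**5. Size of the bias.** Let f be the crossover share, X and N the Crossover and Non-Crossover means at 6 months, and G = X − N. The control mean is M = fX + (1 − f)N, so N − M = −fG. If a fraction r of the gap persists, the later shift of Non-Crossover relative to RDN, with no treatment effect, is −f × G × r.

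From the documents: SD 12 mmHg for change in 24-hour SBP (SAP Table 3), applied here to later visits. Assumed: f = 0.5, correlation of the crossover decision with 6-month BP 0.5, correlation of 6-month with later BP change (r) 0.5, and higher BP favouring crossover. The mean of the upper half of a standard normal is 0.798.

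- G = 2 × 0.798 × 0.5 × 12 = 9.6 mmHg
- Shift = −0.5 × 9.6 × 0.5 = −2.4 mmHg, a quarter of the gap

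**6. Simulation, no treatment effect of any kind.** 166 RDN and 165 control (protocol B.1.2, first interim analysis), SD 12, two-sided 0.05, 3,000 trials for each of 36 scenarios. Assumed: crossover share 25–75%, correlation of 6-month with later change 0.3–0.7, decision correlation 0–0.7.

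| Decision correlation | Three-group ANOVA rejects | RDN vs Non-Crossover rejects | Shift in Non-Crossover, mmHg |
|---|---|---|---|
| 0 | 4.4–5.6% | 4.9–5.4% | about 0 |
| 0.3 | 10.1–48.3% | 5.4–33.0% | −0.4 to −3.2 |
| 0.5 | 22.5–92.0% | 8.3–71.1% | −0.7 to −5.3 |
| 0.7 | 41.7–99.8% | 10.6–96.3% | −1.1 to −7.5 |

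RDN against all randomized control rejected 4.2–6.1% of the time in every scenario, which is nominal within simulation error.

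**7. Sparse events.** With an assumed 50% crossover the smallest group is about 82 of 331. An expected count of 5 there needs 5 × 331/82 = 20.2, so 21 events in total. At 25% or 75% the smallest group is about 41, and 5 × 331/41 = 40.4, so 41 events. The protocol reports one major safety event per arm to 3 months.

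**The case against.** The best defence is that little depends on these tests. Study success rests on the primary safety and efficacy hypotheses alone. The three-group comparisons carry no hypothesis, power or success criterion, and the SAP never claims randomized validity for them. It already stops RDN versus control testing at 6 months, and 9.9.8 and 9.9.9 already plan within-group mean changes with 95% intervals. The documents give no crossover share and no BP by crossover status, so a difference between the subgroups is plausible but not shown. On chi-square, protocol H.1 lets event rates decide between it and Fisher's test, SAP 9.2 names Fisher's test as the general method, and office SBP below 140 mmHg need not be sparse.

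All of this stands, and it limits the stakes. It does not remove the point: the tests are planned, fall under the default 0.05 rule, and carry no descriptive label.

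A reader might infer two stronger claims. The first is that RDN versus Non-Crossover is biased by the entire gap between the control subgroups. Step 5 shows that only the crossover share of the gap enters, and only as far as it persists. The second is that no long-term p-value could be valid. RDN versus all randomized control remains a randomized comparison, of a policy that allows crossover and reintroduced medication, and protocol H.3 and H.6 already plan a comparison between treatment groups.

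**Conclusion.** The point holds for the post-6-month comparisons in SAP 9.9.2, 9.9.8, 9.9.9 and 9.9.10. The p-values for RDN versus Crossover versus Non-Crossover cannot be read as treatment effects, the ITT label is wrong for those tables, and SAP and protocol disagree. This conclusion rests on how the groups are formed, not on the simulation.

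The direction and size of the bias are unknown. The 2.4 mmHg and the rejection rates depend on assumed crossover shares and correlations and show range only. If crossover were unrelated to BP, the BP tests would keep their nominal error rate. A reader should not extend the point to the 3-month powered endpoints or to RDN versus control to 6 months, which are unaffected.

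**What to change.** 1. In SAP 9.9.2, 9.9.8, 9.9.9 and 9.9.10, label the three-group results descriptive: estimates with 95% confidence intervals, exact for events, and no p-values.
2. State each group's time origin and baseline, and how a control subject is classified before a late crossover. Drop the ITT label for these tables.
3. Keep the as-randomized comparison of protocol H.3 and H.6. Add RDN versus all randomized control through 36 months to the SAP as the only formal long-term test, with Fisher's exact test for events. State that it compares policies that allow crossover and reintroduced medication.
4. Because crossover follow-up ends 24 months after the crossover procedure (about month 30 for a month-6 crossover), say which crossover visits stand in for months 24 and 36 and how missing values are handled.

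The cost is SAP wording and a data-mapping rule. The three-group tables lose their p-values. The as-randomized effect will be diluted by crossover, and at 36 months it will rest partly on the rule in item 4.
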